### 10.3. Other Safety Evaluations

#### 10.3.1. Columbia-Suicide Severity Rating Scale (C-SSRS)

The C-SSRS is a low-burden measure of the spectrum of suicidal ideation and behavior that was developed by Columbia University researchers for the National Institute of Mental Health Treatment of Adolescent Suicide Attempters Study to assess severity and track suicidal events through any treatment. It is a clinical interview providing a summary of both ideation and behavior that can be administered during any evaluation or risk assessment to identify the level and type of suicidality present. The C-SSRS can also be used during treatment to monitor for clinical worsening.i The C-SSRS evaluation will be performed as specified in the protocol Schedule of Assessments.

The C-SSRS has 11 binary (yes/no) outcomes corresponding to five categories of suicidal ideation, five categories of suicidal behavior, and the category of self-injurious behavior without suicidal intent:

Suicidal ideation is present if there is a “yes” response to any of the 5 suicidal ideation category questions. Suicidal behavior is present if there is a “yes” response to any of the 5 suicidal behavior category questions. Suicidal ideation or behavior is present if there is a “yes” response to any of the 10 suicidal or ideation or behavior category questions.

Sponsor: Boston Pharmaceuticals, Inc.  
Protocol Number: BOS161721-02  
SAP Version and Date: Version 3.0, 13Nov2020

The number and percentage of patients with any post-baseline occurrence of the following ideations and behaviors will be presented overall, by study phase and treatment group:

- Suicidal ideation (overall and by individual question),
- Suicidal behavior (overall and by individual question),
- Suicidal ideation or behavior,

A similar tabulation of the occurrence of any of the above ideations and behaviors at baseline or as part of their lifetime history/past 12-month history (collected at the screening visit) will be presented overall, by study phase, and treatment group.

A shift table displaying the shift from worst pre-treatment category to the worst post-baseline category will be presented overall, by study phase, and treatment group. Best to worst C-SSRS category is defined in the following order: no suicidal ideation or behavior, suicidal ideation, and suicidal behavior. The worst post-baseline shift is calculated based on all post-baseline visits, including unscheduled visits. Worst pre-treatment will include all C-SSRS assessments prior to first dose date/time (screening or baseline). The denominator will be the number of patients with at least one non-missing baseline and post-baseline C-SSRS assessment.

Missing data will not be imputed.

All C-SSRS individual items will be presented in data listings for screening and post-screening (since last visit), separately. A separate listing will be presented for patients with suicidal ideation, suicidal behavior, or non-suicidal self-injurious behavior for all randomized patients.

#### 10.3.2. Vital Signs

Vital signs include: heart rate (beats/min); temperature (°C); systolic and diastolic blood pressure (mmHg). Observed values, changes, and percentage changes from baseline for vital signs will be summarized at each visit and time point, as well as for most extreme change overall, by study phase, and treatment group.

All vital signs data will be presented in patient data listings for all randomized patients.

#### 10.3.3. 12-Lead Electrocardiogram (ECG)

ECG will be assessed as specified in the protocol Schedule of Assessments. The following ECG parameters will be collected: PR interval (msec), QRS interval (msec), RR interval (msec), QT interval (msec), and QT interval corrected for heart rate using Fridericia's formula (QTcF) (msec). ECG parameters and ECG evaluation will come directly from the database and will not be calculated during analysis.

Observed values, changes, and percentage changes from baseline for ECG parameters will be summarized at each visit, as well as for most extreme change overall, by study phase, and treatment group.

Sponsor: Boston Pharmaceuticals, Inc.  
Protocol Number: BOS161721-02  
SAP Version and Date: Version 3.0, 13Nov2020

The number and percent of patients with the following parameters at any post-baseline visit and at each visit will be summarized:

- Abnormal, not clinically significant ECGs
- Abnormal, clinically significant ECGs

The number and percent of patients with each ECG evaluation result will be summarized by visit. The worst ECG evaluation at any post-baseline visit will also be summarized in the order of: Normal, Abnormal, not clinically significant, Abnormal, clinically significant.

For the summary of incidence at any post-baseline visit, the denominators for percentages will include patients with one or more non-missing value at any post-baseline visit. For the by-visit summaries, the denominators for percentages will include patients with a non-missing value at that visit.

Investigator reported ECG result shifts from baseline to each visit and worst case post-baseline will be summarized. Worst case post-baseline will be based on the most abnormal observed value on or after the randomization date.

All ECG data will be presented in a by patient data listing for all randomized patients. A separate by patient listing for patients with abnormal, clinically significant 12-lead ECGs will also be provided in the safety analysis set for DMC meetings and the interim analysis only.

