### 10.1. Adverse Events

AEs will be collected and recorded for each patient from the date of the first dose of study drug until the end of their participation in the study, including the safety follow up period. Severity of adverse events will be graded by the investigator according to National Cancer Institute Common Terminology Criteria for Adverse Events (NCI CTCAE) version 4.03. AEs will also be assessed for relationship to study drug, and seriousness. Adverse events will be marked as AESIs, dose-limiting toxicities (DLTs), or injection site reactions (ISRs), where applicable. AEs will be considered treatment-emergent adverse events (TEAEs) if they started any time after first dose or if the year, month and day of start date were missing. Any missing severity assessments will be assumed to be Grade 3, missing relationship assessments will be assumed to be related, and missing seriousness assessments will be assumed as serious.

Sponsor: Boston Pharmaceuticals, Inc.

Protocol Number: BOS161721-02

SAP Version and Date: Version 3.0, 13Nov2020

An overview of TEAEs will be produced, including counts and percentages of patients with any incidences of TEAE, TEAEs related to study treatment, SAEs, SAEs related to study treatment, any CTCAE grade 2 or higher TEAEs, any CTCAE grade 2 or higher TEAEs related to study treatment, any CTCAE grade 3 TEAEs, any CTCAE grade 3 or higher TEAEs related to study treatment, any CTCAE grade 4 TEAEs, any CTCAE grade 4 or higher TEAEs related to study treatment, TEAEs leading to study treatment discontinuation, treatment related TEAEs leading to study treatment discontinuation, TEAEs of special interest, related TEAEs of special interest, DLTs, related DLTs, TEAEs resulting in death, related TEAEs resulting in death, and injection site reactions. The maximum CTCAE grade (Grades 1-5) will also be included on the summary table.

Adverse events will be coded based on the MedDRA. Patients will be counted once per SOC (and likewise for PT within SOC). TEAEs will be summarized by SOC and PT in descending order of overall incidence of SOC (and PT within SOC). The MedDRA version used is defined in the study data management plan.

Summaries of adverse events by SOC and PT will include the following types:

- TEAEs;
- TEAEs related to study treatment;
- SAEs;
- Related Serious TEAEs;
- CTCAE Grade 3 or higher TEAEs;
- CTCAE Grade 3 or higher TEAEs related to study treatment;
- TEAEs leading to treatment discontinuation; and

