## 5.2. Reference Dates

- Screening date is defined as the CRF provided date on which a patient was screened for trial entry.
- Randomization date is defined as the date on which the patient is randomized to study treatment.
- Treatment start date is defined as the date of first dose of study drug.
- Treatment end date is defined as the date of last dose of study drug.
- Age will not be calculated and will come directly from the CRF. The CRF uses the informed consent date as its reference date for age calculation.
- Safety data, such as AEs and laboratory assessments will use the treatment start date as a reference date.
- Efficacy data will use the randomization date as a reference date.
- Study day will be based on treatment start date as a reference date.

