#### 5.5. Baseline, Post-Baseline Changes, and Last Observation Carried Forward (LOCF)

Unless stated otherwise, baseline and post-baseline change values will be based on the following:

- Baseline will be based on the last non-missing value collected prior to or on the treatment start date (and time, if applicable).
- Post-baseline values will be those collected after the date/time of first dose of study drug.
- Change from baseline is defined as: value – baseline value.
- Most extreme change: The maximum most extreme change will be the maximum post-baseline value; the minimum most extreme change will be the smallest post-baseline value. This calculation will consider all assessments collected after the first dose of study drug, scheduled or unscheduled.

LOCF will be based on the last non-missing value collected. This calculation will consider all assessments, scheduled or unscheduled, including baseline. If a patient withdraws from the study, their most recent non-missing assessment prior to withdraw will be carried forward. Additional details regarding LOCF for specific endpoints are provided in Section 7.

Observed values do not incorporate any imputations and are presented as collected.

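### SAP v3.0 Section 10.3.3 opens the worst-case post-baseline ECG window at randomization, not first dose, so a pre-dose baseline ECG can qualify as post-baseline

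*SAP*

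**What the plan says.** Section 10.3.3 of SAP v3.0 plans this table: "Investigator reported ECG result shifts from baseline to each visit and worst case post-baseline will be summarized". The window for its worst-case column is then set: "Worst case post-baseline will be based on the most abnormal observed value on or after the randomization date". The window includes the whole randomization day and does not mention first dose. The same sentence stands in Section 10.3.3 of v1.0 and v2.0, which are appended to v3.0.

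The general conventions use a different boundary. Section 5.5 of v1.0 and v2.0 states: "Post-baseline values will be those collected after the date/time of first dose of study drug". It sets baseline as follows: "Baseline will be based on the last non-missing value collected prior to or on the treatment start date (and time, if applicable". For most extreme values it adds: "This calculation will consider all assessments collected after the first dose of study drug, scheduled or unscheduled". Section 5.2 of those versions states: "Safety data, such as AEs and laboratory assessments will use the treatment start date as a reference date". That section defines the randomization date separately and makes it the reference for efficacy data.

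Two safety rules in v3.0 also name first dose. Section 10.1 calls adverse events treatment-emergent "if they started any time after first dose" (or if the start date is wholly missing). Section 10.3.1 states: "Worst pre-treatment will include all C-SSRS assessments prior to first dose date/time (screening or baseline".

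**The concern.** A shift table sets a pre-treatment state against what happened under treatment. It works only if the two windows do not overlap. The ECG sentence lets them overlap whenever an ECG falls between randomization and the first injection, because that ECG can then supply both the row and the column.

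At stake is the worst-case column of a descriptive safety table. ECG results are listed among the safety endpoints of both study parts (Sections 2.1 and 2.2 of v2.0). A pre-existing abnormality that has gone by every post-dose visit would be reported as a post-baseline abnormality. Section 10.3.3 also summarizes each patient's worst evaluation over post-baseline visits without the randomization clause, so two tables built from one section could give different counts.

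**Working it through.** The plan gives no figure to reproduce, so the check compares definitions.

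**Inputs**
- ECG worst-case window: time on or after the randomization date (v3.0 Section 10.3.3).
- General post-baseline window: time after the date and time of first dose (Section 5.5, v1.0 and v2.0).
- Baseline: last non-missing value up to treatment start (Section 5.5, v1.0 and v2.0).
- Severity order of the ECG result: normal (0), abnormal not clinically significant (1), abnormal clinically significant (2) (v3.0 Section 10.3.3).

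**Step 1: difference between the windows.** The ECG window contains everything in the general window plus any ECG from the randomization date up to first dose. Baseline is the last value before dosing. So if any ECG lies in that gap, the baseline ECG lies in it too.

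**Step 2: effect on each cell.** Let B be the baseline result and W the worst result after first dose. With the baseline ECG admitted, the reported worst value is max(B, W).

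| B | W = 0 | W = 1 | W = 2 |
|---|---|---|---|
| 0 | 0 | 1 | 2 |
| 1 | **1** (should be 0) | 1 | 2 |
| 2 | **2** (should be 0) | **2** (should be 1) | 2 |

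Of the nine combinations, three change: (1,0), (2,0) and (2,1). All three are improvements, and all three move to the no-change diagonal. The three worsening cells, (0,1), (0,2) and (1,2), and the three diagonal combinations keep their values.

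**Step 3: effect on column totals.** The total abnormal post-baseline rises by the patients in (1,0) and (2,0). The total clinically significant rises by those in (2,0) and (2,1). A summary restricted to post-dose visits would not include these additions, which is how the two worst-ECG displays can differ.

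**Step 4: size.** Let s be the share of patients whose baseline ECG lies in the gap, b the share abnormal at baseline, and r the share of those who are normal at every post-dose ECG. If s is unrelated to the other two, the abnormal post-baseline rate is overstated by s × b × r. The SAP gives none of the three. As pure assumptions, with b from 10% to 30% and r from 20% to 50%:
- s = 1: from 0.10 × 0.20 = 2 percentage points to 0.30 × 0.50 = 15 percentage points.
- s = 0: 0 points, whatever b and r are.

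**Step 5: granularity in Phase 1b.** Section 3.1.1 of v2.0 plans 5 active patients in Cohort 1 and 9 in each of Cohorts 2 and 3. One reclassified patient moves a cohort's rate by 1/5 = 20 points or 1/9 = 11 points.

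**The case against.** The strongest reply is that the sentence is already about post-baseline values. Someone who applies the Section 5.5 definition first would exclude the baseline ECG, and the randomization clause would then be redundant. That reading is possible but not secure. Section 5.5 opens by saying its definitions hold except where another is stated, and the ECG sentence can be taken as such an exception. Section 5 of v3.0 was not available for this check, so it may or may not settle the matter.

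A second reply is that no harm has been shown. ECG timing is left to the protocol's schedule, which was also not available, and nothing in the SAP text seen places an ECG on Day 0 before dosing. Table 7 labels the ADA baseline as a Day 0 pre-dose sample, which shows that such sampling occurs in this trial, but it says nothing about ECGs. This reply stands: the miscount is conditional.

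A third reply is that the reach is narrow. The clause governs one column of one descriptive table. The by-visit results, the by-visit shifts, the incidence over post-baseline visits and the numeric extreme changes are worded without it, and no hypothesis test on ECG is described. This also stands.

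A reader might infer that the rule conceals real cardiac deterioration. Step 2 shows that adding the baseline ECG cannot alter a worsening cell. A reader might also infer that every other safety rule in v3.0 names first dose. Only the TEAE and C-SSRS rules do so in the text seen; the laboratory and vital-sign sections refer to post-baseline values or extreme changes without restating the boundary.

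**Conclusion.** The inconsistency is real and is in the current text. As written, the v3.0 ECG rule can admit the baseline ECG as a post-baseline value. That conflicts with the general definition in Section 5.5 of the appended versions and with the first-dose anchor used for TEAEs and C-SSRS in v3.0.

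The consequence depends on an ECG being taken on or after the randomization date and before first dose. Where that happens, the improvement cells are empty by construction, patients abnormal only before dosing are counted as abnormal post-baseline, and the table can disagree with the worst-evaluation summary in the same section. Where all pre-dose ECGs precede the randomization date, the effect is zero.

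The documents do not support three stronger conclusions. They do not show that the table will in fact count pre-treatment findings, because the schedule is not in the SAP. They do not support any particular percentage; the 2 to 15 points in the working are an illustration with a true lower bound of 0. They do not show bias between arms, because the same rule applies to both.

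**What to change.** In Section 10.3.3, replace the randomization-date clause with the boundary from Section 5.5: "Post-baseline values will be those collected after the date/time of first dose of study drug". Add that an ECG on the treatment start date without a recorded time counts as pre-dose, which agrees with the Section 5.5 baseline rule. Use the same derived worst value for the shift table and for the worst-evaluation summary, so that the two must agree. Confirm at the same time that Section 5 of v3.0 keeps the first-dose definition.

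The cost is one phrase and one added sentence in the SAP, and a change to one derivation if the table is already programmed. Data collection, endpoints and the other analyses are untouched. Blinded data are enough to count the patients whose worst ECG differs between the two definitions, which would show whether the change affects any reported number.

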#### 10.3.4. Physical Examinations

Targeted physical examination data and full physical examination data will be presented in patient data listings. A separate by patient listing for patients with abnormal, clinically significant physical examination findings will also be provided in the safety analysis set for DMC meetings and the interim analysis only.

### 11. CHANGES TO THE PLANNED ANALYSIS

The following changes were made to the planned analyses:

- Time to SRI-4 Response was originally a planned endpoint for the MAD and POC portions of the study. This was removed from the POC portion of the study upon Protocol Amendment 6 (30Apr2020); however, the endpoint was inadvertently maintained in the protocol for the MAD portion of the study. This analysis will not be performed for any study part.
- Rules for applying LOCF were vague within the protocol and were further detailed in this SAP. See Section 7 for further details.
- The PP was clarified to include additional criteria beyond the protocol description. The PP will exclude patients with more than one missed dose.

Sponsor: Boston Pharmaceuticals, Inc.

Protocol Number: BOS161721-02

SAP Version and Date: Version 3.0, 13Nov2020

- Cytokine, chemokine and genotyping data were originally planned to be part of the MAD and POC portion of the study; however, data for these parameters is only available for the MAD portion of the study.
- The definition of the CLASI response in the protocol is vague as the protocol defines the CLASI response as 50% improvement from baseline in “A” (total activity) or “B” (total damage) scores. The SAP further clarifies the CLASI response as 50% improvement from baseline in CLASI and distinguishes a CLASI-A response from a CLASI-B response.

## 13. APPENDICES

### 13.1. COVID-19 Impact and Data Handling

The COVID-19 Pandemic resulted in contingency plans for BOS161721-02.

- **Safety Oversight:** In case a patient cannot return to the study site for the scheduled visit, the site staff will contact the patient remotely for safety follow up, for example, via telephone or video conferencing. The analysis of safety data will include all collected data regardless of remote data collection.
- **Central Laboratory:** In the case of courier issues that will prevent the protocol-required laboratory specimens to be sent to the study core laboratory, the site should have the safety laboratory specimens (Hematology, Chemistry, and Urinalysis) sent to their local laboratory for analysis and review by the study physician. The local laboratory data will not be entered into the clinical database or analyzed/presented in data summaries.
- **Investigational Product Dosing:** In cases when dosing cannot be performed during the protocol-designated windows, the Investigator should discuss each case with the Sponsor to determine whether it is a missed visit or whether the dosing can be performed outside protocol windows (as a protocol deviation). A minimum of 2 weeks must be maintained between consecutive doses. Patients who miss more than 2 doses of the study drug (whether consecutive or not) will be discontinued from the study and will undergo assessments as outlined in Section 5.5 of the study protocol (Premature Discontinuation). A sensitivity analysis of SRI-4 response using LOCF for missing data and/or observed case data may be performed to assess the impact of patients that did not follow the original protocol dosing schedule.

An addendum to this SAP will be developed that documents all additional data handling techniques employed to manage COVID impacted data, if needed, prior to database lock and unblinding.

Sponsor: Boston Pharmaceuticals, Inc.  
Protocol Number: BOS161721-02  
SAP Version and Date: Version 3.0, 13Nov2020

### 13.2. Physician's Global Assessment

Subject ID: \_\_\_\_\_ Patient Initials: \_\_\_\_\_ Date: \_\_\_\_/\_\_\_\_/\_\_\_\_ Visit: \_\_\_\_

### **PHYSICIAN'S GLOBAL ASSESSMENT (PGA)**

How do you assess your subject's current disease activity?

Result: \_\_\_\_\_ mm

Note: Please review the scale from previous visit, as applicable, and mark a vertical line on the scale above to assess the overall status of the subject's SLE signs and symptoms, and the functional capacity. Zero (0) = very good, asymptomatic and no limitation of normal activity; Three (3) = most severe possible disease ever seen in all SLE patients.

|                        |                   |      |
|------------------------|-------------------|------|
|                        |                   |      |
| Investigator Signature | Assessor Initials | Date |

### 13.3. SLEDAI-2K Index

|   |  |                        |  |
|---|--|------------------------|--|
| Subject Number: _____ - _____   |  |                        | Protocol BOS161721-02  |
| Screening / Randomization / _____ Week Visit & Date of Assessment: _____ - _____ - 20
<small>(Circle visit type &/or enter visit week)</small>       |  |                        | (Day) _____ Month _____ Year _____   |
| SLEDAI 2K Index
Must be present at the time of visit or in the preceding 30 days (or 10 days for V1 and V2) and SLE-Related to be checked! |  |                        |  |
| Wt  | (  ) if Present | Descriptor             | Definitions
If descriptor is checked as present, please check appropriate condition(s) in definition and/or specify in the space provided.   |
| 8   |                            | Seizure                | Recent onset (last 28 days). Exclude metabolic, infectious or drug causes. Specify if checked:  |
| 8   |                            | Psychosis              | Altered ability to function in normal activity due to severe disturbance in the perception of reality. Include:  hallucinations,  incoherence,  marked loose associations,  impoverished thought content,  marked illogical thinking, and  bizarre, disorganized, or catatonic behavior. Exclude uremia and drug causes.   |
| 8   |                            | Organic Brain Syndrome | Altered mental function with  impaired orientation, memory or other intellectual function (with rapid onset and fluctuating clinical features),  inability to sustain attention to environment, and at least 2 of the following:  perceptual disturbance,  incoherent speech,  insomnia or daytime drowsiness,  increased or decreased psychomotor activity. Exclude metabolic, infectious or drug causes. |
| 8   |                            | Visual Disturbance     | Retinal changes of SLE. Include  cytoid bodies,  retinal hemorrhages,  serous exudate or hemorrhages in the choroid, and  optic neuritis. Exclude hypertension, infection, or drug causes.   |
| 8   |                            | Cranial Nerve Disorder | New onset of  sensory or  motor neuropathy involving cranial nerves.   |
| 8   |                            | Lupus Headache         | Severe, persistent headache. May be migrainous, but must be nonresponsive to narcotic analgesia. (Must have been severe enough to warrant lumbar puncture and/or MRI or head CT, perhaps hospitalization, and is thought to be due to active lupus cerebritis.) Specify if checked:   |
| 8   |                            | CVA                    | New onset of cerebrovascular accident(s) (CVA). Exclude arteriosclerosis. Specify if checked:   |
| 8   |                            | Vasculitis             |  Ulceration,  gangrene,  tender finger nodules,  periungual infarction,  splinter hemorrhages, or  biopsy or  angiogram proof of vasculitis.   |

Sponsor: Boston Pharmaceuticals, Inc.

[figure not shown]
Protocol Number: BOS161721-02

SAP Version and Date: Version 3.0, 13Nov2020

|   |                          |                       |   |
|---|--------------------------|-----------------------|---|
| Subject Number _____ - _____  |                          |                       | Protocol BOS161721-02   |
| Screening / Randomization / _____ Week Visit & Date of Assessment: _____ - _____ - 20
(Circle visit type &/or enter visit week) (Day) - (Month) Year |                          |                       |   |
| 4   |  | Arthritis             | ≥ 2 joints with pain and signs of inflammation (  tenderness,  swelling or  effusion). (Complete Joint Count if checked.)                     |
| 4   |  | Myositis              | Proximal muscle aching/weakness associated with  elevated creatine phosphokinase (CK)/aldolase or  EMG changes or  a biopsy showing myositis. |
| 4   |  | Urinary Casts         | Heme-granular or red blood cell casts. (See labs)   |
| 4   |  | Hematuria             | >5 RBC/high power field. Exclude stone, infection, or other cause. (See labs)   |
| 4   |  | Proteinuria           | >0.5 gm/24-hour equivalent. (See labs)  |
| 4   |  | Pyuria                | >5 WBC/high power field. Exclude infection. (See labs)  |
| 2   |  | Rash                  | Inflammatory-type rash. Specify and complete CLASI if checked:  |
| 2   |  | Alopecia              |  Abnormal,  patchy or  diffuse loss of hair. (Complete CLASI if checked.)   |
| 2   |  | Mucosal Ulcers        |  Oral or  nasal ulcerations. (Complete CLASI if checked.)   |
| 2   |  | Pleurisy              | Pleuritic chest pain with  pleural rub or  effusion, or  pleural thickening.  |
| 2   |  | Pericarditis          | Pericardial pain with at least one (1) of the following:  rub or  effusion, or  ECG or  echocardiogram confirmation.  |
| 2   |  | Low Complement        | Decrease in CH50, C3 or C4 below the lower limit of normal for testing laboratory. (See labs)   |
| 2   |  | Increased DNA Binding | >25% binding by Farr assay or above normal range for testing laboratory. (See labs)   |
| 1   |  | Fever                 | >38°C (100.4F). Exclude infectious cause. Specify if checked:   |
| 1   |  | Thrombocytopenia      | <100,000 platelets/mm  (See labs)   |
| 1   |  | Leukopenia            | <3,000 white blood cells/mm  . Exclude drug causes. (See labs)  |
| TOTAL SCORE (Sum of all of weights next to descriptors marked present)  |                          |                       |   |
|   |                          |                       |   |
| Investigator Signature  |                          |                       | Date  |

